5. STATISTICS AND QUANTITATIVE DATA ANALYSIS

5.1 Sample Size

Previous meta-analyses suggest weight gain prevention interventions achieve effects of ~1.5kg at 12 months (less weight gain compared with controls). Our feasibility trial observed a -3.86kg (95%CI: -7.83 to 0.11kg, p=0.06) difference in weight at 6 months between SWiM participants and standard care, with SWiM participants losing ~2.2kg whereas standard care participants gained ~2.2 kg. Our expert elicitation workshop identified a potential mean difference of -1.96kg at 12 months with considerable uncertainty. Pre-trial modelling suggests interventions achieving these differences in weight regain after weight loss, and potentially even smaller differences, should be cost-effective. Thus, we designed the trial to detect a small overall effect size of ~1kg.

With 1,840 participants there is 90% power to detect a 1.01 kg difference in mean weight between SWiM and standard care as significant at the 2-sided 5% level, assuming a standard deviation at baseline of 22 kg, a 0.967 correlation between baseline and follow up 46 and 30% attrition. The correlation between baseline and follow up is based on the SWiM feasibility study, and is corroborated by data from our previous studies including weight change in the first year after finishing a weight loss programme in the WRAP trial (r=0.96) and 9 month weight change in Fenland COVID (N=1162 adults with overweight/obesity, r=0.972).

Designing the trial to detect a small weight difference in the overall sample should also allow a reasonable level of power to detect differences between SWiM and control within each WLP group (e.g. among only those who lost weight with a tier 3 programme), or within specific demographic groups (e.g. among men). Assuming approximately 368 participants from each WLP, there would be 80% power to detect a 1.96kg difference as significant at the 5% level between SWiM and standard care within each WLP.

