5.2 Analysis Plan

A detailed statistical analysis plan will be developed, signed off by the Trial Steering Committee and uploaded to the ISRCTN registry prior to analysis. The intervention effect on 12-month weight change will be estimated from a 2-level mixed effects model, using weight measurements at baseline, 6 and 12 months. The model will include timepoint, intervention-by-timepoint interaction, gender and WLP as fixed effects and random intercepts to allow for repeated measures. This model assumes missing outcome data are missing at random. The primary analysis will include all available data; in a sensitivity analysis, we will impute missing values of the outcome using multiple imputation by chained equations.

Similar analyses will be performed for secondary outcomes. We aim to analyse and publish findings as soon as 12-month follow-up is complete to ensure timely communication of findings and enable analyses of inequalities in engagement and effectiveness and other determinants that we can use to understand adaptations needed; therefore 24-month values are not included in the primary analysis but will be analysed and published separately.

The primary analysis will be repeated to identify potential interactions between the intervention effect and WLP by including a three-way interaction (trial intervention x WLP x timepoint). The 12month intervention effect and 95%CI will be estimated within each WLP. Similar methods will be used to identify potential inequalities by PROGRESS Plus criteria²⁵.

Cost-effectiveness analysis

A detailed Health Economics and Modelling analysis plan (HEDMAP) will be developed and signed off by the Trial Steering Committee. The intervention effect on health-related quality of life will be estimated from a mixed effect model EQ-5D measurements taken at 0, 6 and 12 months.

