7.1 Fidelity in programme delivery

A fidelity assessment will be conducted to evaluate whether SWiM is delivered as intended by the SWiM coaches. Underpinned by Ontological Realism and Epistemology Post-Positivism, this assessment will address the following research question:

To what extent is SWiM delivered as intended?

Data will be collected via observations of session recordings. At a minimum, we intend to recruit six coaches for programme delivery and observe a sample of two complete courses (one course \approx four coach calls) across all six coaches, equating to twelve samples (total N=48 coach calls). If additional coaches are recruited, further observations will be governed by a process of information power. A checklist of core SWiM session parameters (e.g., duration) and content will be developed by the programme development team. The checklist will be assessed for interrater reliability using a sample of session recordings, observed and coded by two researchers individually and in duplicate. This will inform checklist refinements before the full-scale fidelity assessment.

All session recordings will be observed and coded against the refined checklist individually and in duplicate by two researchers. Inter-rater reliability will be analysed and reported and all discrepancies between the two coders will be resolved through discussion. Data will be analysed descriptively to report the degree of fidelity.

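### A random intercept as the only device for repeated weights assumes equal correlation between all visits; if weight correlations decay with time, the 12-month standard error is too small

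*Protocol*

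**What the plan says.** Protocol section 5.2 states that the 12-month effect "will be estimated from a 2-level mixed effects model" using weight at 0, 6 and 12 months. Besides timepoint and the intervention-by-timepoint interaction, the model has "gender and WLP as fixed effects and random intercepts to allow for repeated measures". Random intercepts are the only device named for the correlation between visits; the section mentions no random slope, residual covariance structure or robust standard error. It says that secondary outcomes will be handled in a similar way, and it leaves further detail to a statistical analysis plan.

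Section 5.1 bases the sample size on "a standard deviation at baseline of 22 kg" and "a 0.967 correlation between baseline and follow up", without naming the visit, plus 30% attrition. The 0.967 comes from the feasibility study. Two outside figures are offered in support: "weight change in the first year after finishing a weight loss programme in the WRAP trial (r=0.96"), and 0.972 for nine-month change in another cohort. No 6-to-12-month correlation is given.

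**The concern.** A random intercept with independent, equal-variance residuals is a compound-symmetry model. It takes 0–6, 6–12 and 0–12 month changes to be equally variable and estimates one residual variance from all of them. With complete data that estimate is the average (V06 + V612 + V012)/6, where V is the variance of change between two visits. The 12-month contrast needs V012/2. If people drift apart in weight after a programme, V012 exceeds the average and the reported standard error is too small.

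At stake is the calibration of the confirmatory test and of the 12-month confidence interval. The sample size uses the analysis-of-covariance formula, which needs only the baseline to follow-up correlation. The planned analysis could therefore report more precision than the design provides.

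**Working it through.** **Inputs from section 5.1.** N = 1,840 at 1:1, SD 22 kg, r = 0.967, attrition 30%, two-sided 5%, difference 1.01 kg.

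**The plan's own figure.** Analysed per arm: 1,840 × 0.70 / 2 = 644. Residual SD = 22 × √(1 − 0.967²) = 5.605 kg. SE = 5.605 × √(2/644) = 0.312 kg. Power = Φ(1.01/0.3124 − 1.960) = Φ(1.273) ≈ 89.9%. The protocol's statement, "With 1,840 participants there is 90% power to detect a 1.01 kg difference in mean weight", reproduces.

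**Type I error under a random intercept.** Take equal SDs at all visits and write r06, r612 and r012 for the three correlations. With no intervention main effect in the model, baseline means are constrained equal. For complete data in large samples:

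- The random-intercept fit estimates a single correlation r̄ = (r06 + r612 + r012)/3.
- Model-based variance of the 12-month effect ∝ 1 − r̄².
- True variance of the same estimator ∝ 1 + r̄² − 2·r̄·r012.
- Actual alpha = 2 × [1 − Φ(1.96 × SE ratio)], where SE ratio = √[(1 − r̄²)/(1 + r̄² − 2·r̄·r012)].

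Worked case, r06 = r612 = 0.975 and r012 = 0.967: r̄ = 0.97233. Model term 1 − 0.94543 = 0.05457. True term 1 + 0.94543 − 1.88049 = 0.06494. SE ratio = √(0.05457/0.06494) = 0.917, so alpha = 2 × [1 − Φ(1.797)] = 7.2%.

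Only 0.967, 0.972 and 0.96 stand in the protocol. Their assignment to visit pairs, and every other value below, is an assumption.

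| r06 | r012 | r612 | r̄ | SE ratio | Alpha |
|---|---|---|---|---|---|
| 0.967 | 0.967 | 0.967 | 0.96700 | 1.000 | 5.0% |
| 0.967 | 0.967 | 0.972 | 0.96867 | 0.975 | 5.6% |
| 0.967 | 0.967 | 0.980 | 0.97133 | 0.933 | 6.8% |
| 0.967 | 0.960 | 0.967 | 0.96467 | 0.941 | 6.5% |
| 0.967 | 0.960 | 0.980 | 0.96900 | 0.882 | 8.4% |
| 0.975 | 0.967 | 0.975 | 0.97233 | 0.917 | 7.2% |
| 0.9834 | 0.967 | 0.9834 | 0.97791 | 0.820 | 10.8% |
| 0.967 | 0.967 | 0.955 | 0.96300 | 1.058 | 3.8% |

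The value 0.9834 is √0.967, the adjacent correlation under first-order autoregressive decay.

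**With dropout.** Assume 15% are lost before 6 months and a further 15% before 12 months, N = 1,840. Model-based against true SE for the 12-month effect:

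- all correlations 0.967: 0.306 v 0.306 kg, alpha 5.0%;
- adjacent 0.975, r012 = 0.967: 0.279 v 0.304 kg, alpha 7.2%;
- adjacent 0.9834, r012 = 0.967: 0.248 v 0.302 kg, alpha 10.8%.

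The 0.967/0.96 rows become 6.5–7.7%, and the 0.955 row 4.3%.

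**Simulation.** 1,500 trials per scenario under the null, REML random-intercept fit, same dropout: 5.1%, 6.5% and 11.5% for the three listed scenarios. The mean model SE (0.306, 0.279, 0.248) and the spread of the estimates (0.307, 0.305, 0.304) agree with the formula.

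**After the fix.** With an unstructured covariance and r012 = 0.967, the SE is about 0.30–0.31 kg, alpha is 5% and power for 1.01 kg stays at about 90%. If r012 were 0.96, the SE would be about 0.33–0.34 kg; that follows from the lower correlation, not from the choice of covariance.

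**The case against.** **The inflation is not established for this trial.** A reader might infer that the true type I error is 7–11%. The documents do not support that as a flat statement. Under the single design correlation of 0.967 the error is exactly 5%, and 11% needs an adjacent correlation of about 0.983, which appears nowhere in the protocol. This objection stands in full, so the size can only be given conditionally.

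**The quoted correlations do not demonstrate decay.** It is tempting to read 0.972 at nine months against 0.96 at one year as decay. They come from different studies in different populations. The design value of 0.967 comes from a feasibility study whose only quoted weight result is at 6 months; if it is a 6-month correlation, the sequence 0.967, 0.972, 0.96 is not monotone. This also stands. Stronger correlation between adjacent visits remains plausible for weight, but it is a judgement.

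**The analysis plan may settle it.** Section 5.2 does not exclude a residual structure or robust standard errors. That is fair, and it lowers the urgency. However, the section does name a device for the repeated measures, and following it with default residuals gives compound symmetry.

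**Two further readings go too far.** One is that sharing coaches adds a quantifiable inflation: section 7.1 says "we intend to recruit six coaches for programme delivery", but as a minimum, and no intracluster correlation is given, so no error rate can be attached. The other is that the problem must be worse at 24 months: no correlations for that visit are given, and the 24-month values are analysed separately.

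**Conclusion.** The point holds in conditional form. The repeated-measures structure in section 5.2 is valid for the 12-month standard error only if weight changes over 0–6, 6–12 and 0–12 months are, on average, as variable as the 0–12 month change alone. Equal correlation and equal variance at all visits would ensure this, but nothing in the protocol shows it. Departures in the plausible direction make the test too liberal; the opposite pattern makes it slightly conservative.

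The results assume equal SDs over time and, where dropout is modelled, dropout unrelated to weight. The sample size calculation is unaffected and reproduces, and no bias in the estimated effect has been shown. For HbA1c and the questionnaire outcomes the protocol gives no correlations, so neither the size nor the direction of any error can be stated. This is an inexpensive improvement to the primary analysis, not a demonstrated failure of it.

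**What to change.** In section 5.2, and in the statistical analysis plan before analysis, replace the random intercept with an unstructured residual covariance over baseline, 6 and 12 months, fitted by REML as a constrained-baseline mixed model for repeated measures. The listed fixed effects can stay. Apply the same structure to the secondary outcomes.

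If the random intercept is kept, use at least cluster-robust standard errors at participant level. This is the weaker option: it repairs the standard error, but with dropout the missing-at-random justification still leans on a correctly specified covariance.

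Cost: one sentence and four more covariance parameters (six instead of two), with 1,840 × 0.70 = 1,288 participants expected at 12 months. The reported standard error may be larger than under the random intercept, for example about 0.30 instead of 0.25–0.28 kg in the adjacent-correlation scenarios with r012 = 0.967. That is in line with the 0.312 kg behind the sample size. The unstructured model contains the stated one as a special case, so nothing material is lost if equal correlation turns out to be right.

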3.3.3 Study measures

Participants will complete online assessments at baseline (0 months), 6, 12, and 24 months. Details of which measures will be taken at each appointment are summarised in Table 1. Participants will be given a gift voucher for completing online assessments (£10 for the 6-month assessment, £20 each for the 12- and 24-month assessments). Honoraria for assessment completion are independent of intervention attendance or completion. Where participants are unwilling to complete the full assessment, a reduced amount (£10) will be offered for completion of a minimal data questionnaire (primary outcome and key process data).

Table 1. Schedule of Enrolment, Interventions, and Assessments

	STUDY PERIOD				
	Enrolment	Baseline	Follow Up		
TIMEPOINT**	-t ₁	0	6 months	12 months	24 months
ENROLMENT:					
Eligibility screen	Х				
Informed consent		Х			
Randomisation		X (after baseline assessmen t)			
INTERVENTIONS:					
Supporting Weight Maintenance (SWiM)		•	-		
Standard Care		Х			
ASSESSMENTS:					
Height		Х			
Weight		Х	Х	Х	Х

Self-Report Questionnaires	Х	Х	Х	Х
HbA1c	Х	Х	X	X

Weight

At baseline, participants will be asked to report their height, and measure and report their weight, on the day that they complete the outcome assessment. Participants will be provided with a set of weighing cellular-scales (Withings BodyPro2). The scales are pre-configured before sending, and report weight measures over cellular data networks, and do not require a wi-fi connection or digital literacy to use. When participants stand on the scales, data is sent automatically to Withings' GDPR compliant servers in the EU and then retrieved using the Withings developer API directly to the MRC Epidemiology Unit's secure research data server. Data transfers are secured using HTTPS and OAuth2.0 authentication. Instructions for self-weighing will be provided to reduce measurement bias. Eligibility screening will assess the suitability of the scales. Participants with a pacemaker, defibrillator, or other electronic implant will receive the BodyPro scale instead, as it does not use bioelectrical impedance. Participants living in areas with poor cellular network connectivity or weighing over 200kg will receive a suitable medical-grade scale and will be contacted by the study team to report their weight. All participants will be asked to self-report weight in questionnaires (see Table 2) at each assessment as a back-up.

HbA_{1c}

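### The one sensitivity analysis named for missing 12-month weights assumes missing at random, as the primary model does, so it cannot test a departure from that assumption

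*Protocol*

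**What the plan says.** Protocol section 5.2 estimates the 12-month effect from a two-level mixed model with random intercepts, fitted to the baseline, 6-month and 12-month weights and using all available data. It states the assumption openly: "This model assumes missing outcome data are missing at random". It then gives one further analysis for missing weights: "in a sensitivity analysis, we will impute missing values of the outcome using multiple imputation by chained equations". It does not say which variables enter the imputation model. No section names a delta-adjusted, pattern-mixture, reference-based or other not-at-random analysis. A detailed statistical analysis plan is promised before analysis.

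Section 5.1 sets the scale: "With 1,840 participants there is 90% power to detect a 1.01 kg difference in mean weight between SWiM and standard care", with 30% attrition allowed for.

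Section 3.3.3 describes home weighing on supplied cellular scales ("When participants stand on the scales, data is sent automatically"), self-reported weight as a back-up, vouchers, and a reduced voucher for a minimal questionnaire that still captures the primary outcome.

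**The concern.** A sensitivity analysis should vary the assumption on which the main result depends. Chained-equations imputation without a shift or pattern term is valid under missing at random, and so is the likelihood-based mixed model. If 12-month weights are missing for reasons tied to those weights themselves, beyond what the recorded data explain, both analyses are biased, and agreement between them is no reassurance.

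This trial has features that make such a departure possible and allow it to differ by arm. Weight is measured at home, so a participant who has regained can simply not step on the scales. Participants know their allocation (sections 3.4 and 14). Only SWiM participants get coach calls, re-engagement calls, a weight tracker and encouragement to weigh weekly (section 4.1); controls get no additional structured support (section 4.2). The target difference is about 1 kg and almost a third of outcomes may be missing, so a modest departure in one arm could change the conclusion while the named check shows nothing.

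**Working it through.** **Inputs (protocol section 5.1).** N = 1,840, allocated 1:1; attrition 30%; baseline SD 22 kg; baseline to follow-up correlation 0.967; two-sided 5%; target difference 1.01 kg.

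**1. Reproduce the plan's own figure.**
- Completers per arm: 1,840 × 0.70 / 2 = 644.
- Baseline-adjusted SD: 22 × √(1 − 0.967²) = 5.605 kg.
- SE of the difference: 5.605 × √(2/644) = 0.312 kg.
- Power at 1.01 kg: Φ(1.01/0.3124 − 1.96) = 89.9%, against the stated 90%. The figure reproduces, so this SE is the one the protocol implies.
- Smallest significant difference: 1.96 × 0.3124 = 0.612 kg.

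**2. Effect of a departure from missing at random.** Let d be the mean amount by which missing participants are heavier at 12 months than the missing-at-random prediction, and a the share missing, in SWiM (S) and control (C). The benefit is overstated by

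a_S × d_S − a_C × d_C.

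With 30% missing in each arm and a departure in SWiM only, this is 0.3 × d. Holding the SE at 0.312 kg, an observed 1.01 kg
- loses significance at d = (1.01 − 0.612)/0.3 = 1.33 kg;
- falls to zero at d = 1.01/0.3 = 3.37 kg.

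| d in SWiM only (kg) | bias (kg) | benefit left (kg) |
|---|---|---|
| 0 | 0 | 1.01 |
| 0.5 | 0.15 | 0.86 |
| 1.0 | 0.30 | 0.71 |
| 1.5 | 0.45 | 0.56 |
| 2.0 | 0.60 | 0.41 |
| 3.0 | 0.90 | 0.11 |

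**3. Cases in which the result holds or the bias is small.**
- Equal d and equal attrition: bias 0.
- Equal d of 2.2 kg with 35% attrition in SWiM and 25% in control: 2.2 × (0.35 − 0.25) = 0.22 kg.
- Missing SWiM participants do no better than control: 0.7 × 1.01 = 0.707 kg, and z = 0.707/0.3124 = 2.26, p = 0.02, still significant.
- A larger observed effect: at 1.5 kg, significance is lost at (1.5 − 0.612)/0.3 = 2.96 kg; at 1.96 kg, at (1.96 − 0.612)/0.3 = 4.49 kg.
- If control non-responders depart more than SWiM non-responders, the sign reverses and the benefit is understated.

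**4. What the two planned analyses do (simulation, 920 per arm, 6-month weight observed for all).**
- *Departure from missing at random.* 30% missing at 12 months in each arm; missing SWiM participants 2.2 kg heavier than predicted; 60 replicates. True difference −0.33 kg, random-intercept model −1.01 kg, multiple imputation −1.00 kg. The two agree, and both are wrong by about 0.68 kg.
- *Missing at random, driven by 6-month regain in SWiM.* About 30% missing in SWiM and 28% in control; 6-month change SD 4.5 kg; further change SD 3.4 kg; 40 replicates. True difference −1.00 kg, random-intercept model −1.40 kg, regression imputation by arm −0.99 kg. Under a second such setting the figures were −1.05, −1.65 and −1.03 kg. The size of the gap depends on how strongly dropout follows 6-month weight.

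The second case shows what the planned imputation is good for; the first shows what it cannot do.

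**The case against.** The strongest objection is scope. A full analysis plan is promised, and shift ranges and tipping points are normal content for it. The protocol does not say that imputation will be the only sensitivity analysis, and it makes no claim of robustness. This stands to the extent that absent detail is no fault. But the protocol does choose a check directly after stating the assumption, and the chosen check keeps that assumption. The point concerns that choice, and the analysis plan may yet supply the remedy.

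A reader might infer that the imputation is redundant because it must agree with the primary model. That is not supported. A random-intercept model forces the 6-month and 12-month weights to be as correlated as baseline and 12 months; chained equations do not. When dropout follows observed 6-month weight, the two can differ by 0.4 to 0.6 kg, with the imputation close to the truth. Section 5.2 also leaves room for auxiliary variables that the primary model lacks.

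A reader might also take the changes of about 2.2 kg in each feasibility arm as evidence that d = 1.33 kg is likely. They are whole-arm changes from baseline at 6 months, whereas d is the gap between missing participants' weights and their predicted weights. The documents give no estimate of d.

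Vouchers, reminders, the minimal questionnaire and back-up self-report should reduce missingness, but the protocol still plans for 30%.

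**Conclusion.** The point holds in limited form. The named imputation is worth doing, but it shares the primary model's missing-at-random assumption and so cannot show whether the conclusion survives a departure from it.

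Under the protocol's planning values, a SWiM-only departure of 1.33 kg in the missing 30% is enough to lose significance at an observed 1.01 kg, and 3.37 kg removes the effect. These thresholds assume 30% missing in each arm, a fixed SE of 0.312 kg, an observed effect equal to the design difference, and no departure in control. Relaxing the last two can raise the thresholds considerably. It would be too strong to say that the trial's result is likely to be biased: bias needs a departure or an attrition rate that differs between arms, which the design makes possible but the documents do not establish.

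**What to change.** Keep the multiple imputation and extend it in the statistical analysis plan, before data are seen:

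- Add shifts to the imputed 12-month weights, for example 0 to +4 kg, varied separately by arm, and report the combinations at which the conclusion changes (the tipping point).
- Add one reference-based scenario in which missing SWiM outcomes follow the control arm.
- Consider between-visit scale readings as auxiliary variables in the imputation, allowing for SWiM participants being encouraged to weigh weekly, so that weighing frequency may differ by arm.

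This needs no new data collection. The cost is a few lines in the plan and a little more programming; the downside is that the resulting robustness statement may be less favourable.
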